10.0 Data Safety Monitoring

The Data Safety and Monitoring Board (DSMB) that monitors virtually all the alcohol studies at IUSM will review this study at least annually. This board is comprised of all IU faculty engaged in IV alcohol research, and chaired by [name], who is independent of the sponsor and investigators. The following will be monitored as part of the Data Safety Monitoring Plan (DSMP): data quality, recruitment, accrual, retention, outcome and adverse event data, assessment of scientific reports or therapeutic development, results of related studies that may impact participant safety, and procedures designed to protect the privacy of participants.

11.0 Study Withdrawal/Discontinuation

The participant may withdraw from the study at any time for any reason. The PI may choose to terminate any subject's participation at any time if it is deemed that s/he cannot participate or cooperate in testing procedures safely or if a subject's behavior jeopardizes integrity of the collected data. Partial days will be compensated at a rate of \$15/hour, including time to recover to a BrAC < 35 mg/dL. Payment will be calculated in 20 min increments.

12.0 Statistical Considerations

The primary goal of the study is to generate data that would be supportive of a large, properly powered study of the effects of OT on tolerance and/or motivation for alcohol. For this exploratory study, we anticipate examining within-subject effects of OT compared to PL using paired t-tests, accommodating baseline assessments as appropriate for the specific measures.

Aim 1 Hypothesis Testing Plan

Hypothesis 1: Tolerance to alcohol will be altered by OT, such that participants exhibit greater effects of alcohol when tested with OT compared to PL and each with respect to its own baseline assessment. Specifically, we predict the following differences in one or more of the following measures:

Stop Signal Response Task: Participants will have more rapid reaction times under PL compared to OT. Subjective Perceptions of Alcohol and Craving Participants will report weaker subjective effects of alcohol and higher craving under PL compared to OT. Stroop Test Participants will have shorter response times and fewer errors under PL compared to OT.

Aim 2 Hypothesis Testing Plan

Hypothesis 2: OT will reduce motivation for alcohol as demonstrated by changes in one or more of the following measures:

Alcohol Purchase Task

Participants will display alteration in behavioral economic indices derived from the Alcohol Purchase task under OT compared to PL (for example, a reduction in intensity, greater elasticity, lower breakpoint, lower total outcome, etc.).

Subjective Perceptions of Alcohol and Craving

Participants will report weaker subjective effects of alcohol and higher craving under PL compared to OT. Alcohol Self-Administration

Participants will demonstrate reduced cumulative work for alcohol rewards and less overall alcohol exposure under OT compared to PL.

Missing Data

Missing data may occur intermittently or due to attrition. Due to the within-subjects design, participants completing only one of two experimental sessions will be excluded from final analyses.

Power Analyses

While OT is a commonly used agent in human studies, this is a novel investigation of the effect of OT on laboratory measures of alcohol tolerance and motivation for alcohol. Consequently, no directly relevant preliminary data exists upon which to base proper power analyses – collection of such data is the primary objective of this investigation. However, our previous alcohol self-administration work showed effect sizes from 0.49 to 1.31 according to the phenotype of interest. Effect size estimates attributable to an alcohol clamp vary considerably in the literature depending on the participant population, exposure, and outcome of interest. For example, we and our colleagues have identified effect size for the differences in alcohol elimination rate in participants stratified by sex is moderate (f2=0.07). We recently identified an alcohol effect on P300 amplitude in response to the stop signal using the clamp (f2 = 0.57). At baseline, we have also documented both large and small sex differences in subjective responses in both general (large effect of f2 = 0.35) and specifically as a function of abstinence (small effect of f2 = 0.034).

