5.0 Study Design

Overview: This project employs a double-blind, within-subject design. Each participant will be randomly assigned to either the clamp or self-administration condition, and be studied twice, once with intranasal administration of OT and once with intranasal PL. At least 3 weeks will elapse between each participant's tests to ensure that residual effects of OT administration have dissipated.

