6.0 Enrollment/Randomization

Participants will be randomized to study session order (OT-PL or PL-OT) at time of scheduling, using a procedure that ensures an equal number of participants in each group. Stratification of other potentially key risk or analytical variables, such as sex and age distribution, will be periodically monitored and individual subject order assignment may be adjusted to achieve balance. Neither subjects nor technicians will know which session is PL, and which is OT.

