Session procedures: Self-administration (Figure 4). During the 150 min alcohol self-administration session, the participant initiates each work-set by choosing between 1 of 2 rewards, either alcohol or water. Work-sets consist of trials of the Constant Attention Task, or CAT (Figure 5), developed by our laboratory and with demonstrated sensitivity to pharmacogenomics and sex effects^{38, 39}. Successive rewards require an increasing number of successful CAT trials. The work schedules required to obtain water or alcohol are identical, but progress is tracked separately and not communicated to the participants. Throughout any workset, participants are free to wait, work ad-lib, pause, or cease working. The available rewards are a standardized increment in BrAC (alcohol, labeled "A") or an infusion of saline (water, labeled "W"), each delivered over 2.5 min. Reward delivery begins immediately after the last correct CAT trial required for the work-set is performed. Alcohol reward increments raise the participant's BrAC by 10.0 mg/dL in 2.5 min before declining at a steady rate of -0.8 mg/dl/min, until the next alcohol reward is delivered or as long as pharmacokinetically possible. CAIS continuously estimates the future time course of BrAC and prohibits infusion that would vield a BrAC exceeding the predetermined, ecologically valid safety limit (180 mg/dL in this heavy alcohol drinking sample). The first dose of OT or PL will be administered 30 min before the start of the self-administration phase, and consist of 10 intranasal puffs [insufflations] alternating every 30 seconds between nostrils, delivering in total 40 IU of OT in 1 ml of solution or 1 ml of PL solution. Booster doses of 24 IU of OT will be given approximately hourly after the initial dose. Participants will complete the subjective perceptions assessment and side effects questionnaire prior to the first OT/PL administration, immediately before the start of alcohol self-administration, and at 20 min intervals throughout the session, timed with alcohol reward increments when possible. Except for ad-libitum bathroom breaks, participants remain in the chamber or room for the duration of the experiment; technician interaction is limited to occasional BrAC samples, data collection, and verbal checks to assure subject comfort at the beginning/end of each intervention.

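### The crossover is randomised by session order but analysed by paired t-tests alone, with order balance not stated within arm and no period-adjusted result or within-order SD planned

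*Combined protocol and SAP*

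**What the plan says.** Section 5.0 sets up a two-session crossover in which "Each participant will be randomly assigned to either the clamp or self-administration condition". Section 6.0 adds that "Participants will be randomized to study session order (OT-PL or PL-OT) at time of scheduling". It promises balance between the orders by "using a procedure that ensures an equal number of participants in each group". The groups there are the two orders. Clamp or self-administration arm is not named as a balancing factor, although section 6.0 also allows individual order assignments to be changed to balance variables such as sex and age. Section 7.0 (Participants) aims for 10-15 completers, at least 5 per arm.

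The only analysis named in section 12.0 is: "we anticipate examining within-subject effects of OT compared to PL using paired t-tests, accommodating baseline assessments as appropriate for the specific measures". Under Missing Data, "participants completing only one of two experimental sessions will be excluded from final analyses". Aim 1 measures are compared "each with respect to its own baseline assessment". The Aim 2 self-administration prediction is "reduced cumulative work for alcohol rewards and less overall alcohol exposure under OT compared to PL", and those two outcomes have no same-session baseline. Section 12.0 gives the study's main purpose as supplying data for a larger, properly powered study.

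**The concern.** In a two-period crossover, a shift common to everyone's second session enters the OT-PL difference with one sign in one order and the opposite sign in the other. A paired t-test ignores this. If the orders are unequal, part of the shift is read as drug effect. Even if they are equal, the shift adds to the spread of the differences, so the SD is too large and the test too conservative. The washout of at least 3 weeks deals with carryover, not with this.

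For clamp measures, subtracting each session's own baseline removes an additive session shift, though not a change between sessions in the alcohol response itself. Cumulative work and BrAC exposure have no such protection. Two features differ by session whatever the order:

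- Session 2 follows experience of a work schedule on which "progress is tracked separately and not communicated to the participants".
- Session 2 pays $200 against $130.

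Task practice is not the route, because the adaptive task holds the success rate constant (section 7.0, Figure 5). The late-stay instruction for session 2 is weak support, because it depends on what happened in session 1 and so possibly on session 1 treatment.

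At stake are the effect estimate and SD that the larger study would be planned on.

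**Working it through.** **Inputs.** The plan has no figure to reproduce: section 12.0 gives no alpha, sidedness, power or SD. From the documents come the minimum of 5 per arm (section 7.0) and effect sizes of 0.49 to 1.31 (section 12.0, Power Analyses; metric not stated, read here as paired). Assumed: two-sided 5%, normal data, and P = 0, 0.25, 0.5 or 1, where P is the session 2 minus session 1 shift in units of the within-order SD of D = OT - PL.

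**Formulas.** Let n1 participants follow OT-PL and n2 follow PL-OT, with n = n1 + n2. D has mean tau - P in the first order and tau + P in the second.

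- Bias of the paired mean: P(n2 - n1)/n.
- Expected variance of D: 1 + kP², with k = 4·n1·n2/[n(n-1)]. At 3:2, k = 24/20 = 1.2, so P = 0.5 gives 1 + 1.2 × 0.25 = 1.30.
- Adjusted estimate: the unweighted mean of the two order-specific means, with SE = ½·s·√(1/n1 + 1/n2) on n - 2 df, where s is the pooled within-order SD.

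| Split | Size of bias | Variance ratio, P = 0.25 / 0.5 / 1 | Paired-test size (%), same P |
|---|---|---|---|
| 3:2 | 0.2P | 1.08 / 1.30 / 2.20 | 4.6 / 3.5 / 1.3 |
| 3:3 | 0 | 1.08 / 1.30 / 2.20 | 4.4 / 3.1 / 0.8 |
| 4:4 | 0 | 1.07 / 1.29 / 2.14 | 4.5 / 3.0 / 0.7 |
| 4:2 | 0.33P | 1.07 / 1.27 / 2.07 | 4.8 / 4.3 / 2.5 |
| 4:1 | 0.6P | 1.05 / 1.20 / 1.80 | 5.4 / 6.4 / 7.4 |

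Sizes come from simulation with 400,000 replicates. The adjusted test holds about 5% throughout. Size also exceeds 5% at 5:1 (8.2% at P = 0.5).

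**How likely is imbalance within an arm?** Assume orders equal overall, arm independent of order, and no losses.

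- Arm of 5 from 10: P(4:1 or worse) = [2·C(5,4)·C(5,1) + 2]/C(10,5) = 52/252 = 20.6%. Of this, 2/252 = 0.8% is 5:0, where period and treatment cannot be separated.
- Arm of 6 from 12: P(4:2 or worse) = 1 - C(6,3)²/C(12,6) = 1 - 400/924 = 56.7%.

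**Power at an effect of 1.31 (%).** The range at 3:2 depends on which order has more participants.

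| Split | Paired, P = 0 | P = 0.25 | P = 0.5 | Adjusted, any P |
|---|---|---|---|---|
| 3:2 | 60 | 54-60 | 43-56 | 50 |
| 3:3 | 73 | 70 | 63 | 67 |
| 4:4 | 89 | 87 | 82 | 87 |

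**Break-even P above which the adjusted result is better.**

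| Criterion | 3:2 | 3:3 | 4:3 | 4:4 |
|---|---|---|---|---|
| MSE of the estimate | 0.46 | identical | 0.38 | identical |
| MSE of the variance estimate | 0.35 | 0.30 | 0.28 | 0.25 |
| CI half-width (RMS) | 0.55 | 0.37 | 0.33 | 0.25 |

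**The case against.** The strongest objection is that P is assumed. No document figure supports 0.5 SD, and at 0.25 or less the paired test is as good or better. Payment is a fixed sum per session, not tied to work done. Most participants are expected to have completed an earlier experiment, which may lessen novelty. This stands, and is why the paired result should be kept.

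The estimate itself barely moves in the likeliest split: at 3:2 and P = 0.5, its MSE is 0.209 paired against 0.208 adjusted. At n = 5 the 95% interval for an SD runs from 0.60 to 2.87 times the estimate, far wider than the inflation of √1.30 = 1.14 at P = 0.5. At an effect of 0.49 and P = 0, neither analysis has useful power (14% against 12% at 3:2). All of this stands. It limits the weight of the point, but sampling error in the SD does not excuse an avoidable upward bias.

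Section 6.0's list of monitored variables is open-ended, so arm could be covered. It is not named, however, and one phrase would settle it. Most of the 56.7% is 4:2 (450/924 = 48.7%), where the test is still conservative; only 8.0% is worse.

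The follow-up might be a parallel-group study, for which neither SD of differences is the planning input. The documents do not say. Lastly, extending the adjusted summary to clamp measures goes beyond the main problem; it guards only against a session change in the alcohol response and has lower priority.

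**Conclusion.** The concern holds, as a change the sponsor should make rather than a fatal flaw. Paired t-tests are the only analysis named, order balance is not stated within arm, and completers-only analysis can upset whatever balance was achieved. An arm of exactly 5 cannot have equal orders at all.

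The size depends on P, which is unknown. Up to about 0.25 SD the effect is negligible. From about 0.5 SD the pilot variance is inflated by roughly 30% or more at 3:2 or 3:3, and a follow-up sized on it would be too large unless it too is analysed by paired t-test. The paired test is generally conservative; of the splits examined, only 4:1 and 5:1 exceed 5%. The imbalance probabilities assume arm independent of order and no dropout. Medium confidence is appropriate, because the omission is clear but its effect cannot be sized from the documents.

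**What to change.** 1. **Section 6.0:** state that session order is balanced within each of the clamp and self-administration arms. This takes one sentence, costs no degrees of freedom, and prevents 4:1 and 5:0 splits except through dropout. It cannot be done after assignment.
2. **Section 12.0:** keep the paired result. Beside it, prespecify the period-adjusted estimate (mean of the two order-specific mean differences) with its 95% CI and the pooled within-order SD. Do this for cumulative work and BrAC exposure and, with lower priority, for baseline-referenced clamp values.
3. **Reporting:** give completers and session differences by order, and offer both SDs as inputs to a follow-up crossover; the paired SD applies if that study is also analysed by paired t-test. State that the adjustment removes only a session effect common to both orders, not any part of the late-stay effect that depends on session 1 treatment.

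The work is one more sentence in 12.0 and a few lines of code. The statistical cost is one degree of freedom. At P = 0 and an effect of 1.31:

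| Split | Power, adjusted v paired | 95% CI half-width (SD), adjusted v paired |
|---|---|---|
| 3:2 | 50% v 60% | 1.45 v 1.24 |
| 4:4 | 87% v 89% | 0.87 v 0.84 |
| 4:1 | 37% v 60% | 1.78 v 1.24 |

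Balancing within arm is therefore worth more than adjusting afterwards, and the adjusted result should accompany the paired one, not replace it.

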2.0 Objective(s)

The goal of this project is to provide evidence supporting the hypothesis that intranasal OT treatment blocks or reduces tolerance to alcohol and motivation for alcohol in heavy drinking individuals. Evidence supporting either outcome would indicate that OT has a potentially novel therapeutic effect and would then be used in a subsequent, larger study of the effect. Such an outcome would open new fields of investigation into a potential role for OT in AUD treatment, notably the prevention of relapse and support of abstinence. This could have profound effect on treatment approaches for AUDs. The project will examine whether OT reverses tolerance and associated alcohol seeking in humans. Tolerance to and motivation for alcohol will be assessed with sensitive tests of subjective response and cognitive function tested prior to, at the beginning, and at the end of an intravenous alcohol BrAC clamp (a standardized brain alcohol exposure). Alcohol seeking will be tested using a progressive ratio alcohol self-administration paradigm, assessing objective change in motivation for alcohol.

2.1 Primary Objective:

Aim 1: Demonstrate that OT alters alcohol tolerance. This will be assessed using a within-subjects design comparing OT and PL infusion sessions. Cognitive, motor and subjective responses will be tested prior to, at the beginning, and at the end of a steady-state alcohol clamp.

2.2 Secondary Objective:

Aim 2: Demonstrate that OT decreases motivation for alcohol. Motivation for alcohol will be measured directly when participants will be able to earn standardized alcohol exposures by performing a button pressing task on a progressive ratio scale in the active versus control condition. Motivation will also be assessed by measures given during the clamp (and its respective baseline and control assessments) including an alcohol purchase task (APT) that assesses the value of alcohol from a behavioral economics perspective and measures of subjective perception and craving for alcohol.

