3.0 Outcome Measures/Endpoints

3.1 Primary Outcome Measures:

Aim 1: OT will alter alcohol tolerance. Compared to their performance under PL and respective baseline assessment, participants given intranasal OT will show, in one or more of the following, greater alcohol-related perturbation of the subjective response to alcohol, the Stroop test, and Stop Signal task performance.

3.2 Primary Outcome Measures:

Aim 2: OT will reduce motivation for alcohol. Participants will display lower motivation for alcohol under OT compared to PL, reflected by one of more of the following: During alcohol self-administration, less cumulative work for alcohol on the progressive ratio task, and reduced overall alcohol exposure as reflected by the breath alcohol concentration (BrAC) curve during alcohol self-administration; During the BrAC clamp, altered APT derived behavioral economic indices and/or reduced subjective craving for alcohol.

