Figure 3: Alcohol Clamp. Diagram of the experimental session showing test batteries (orange boxes), OT and PL administrations (green boxes), alcohol clamp (grey box) and example subject breath alcohol concentrations (colored lines). **Experimental timeline:** Min 0-30: Baseline battery. Min 30-35: Intranasal OT or PL administered. Min 35-60: Pause for drug absorption. Min 60-90: OT/PL battery. Min 90-105: OT/PL booster dose at the beginning of a 15 min alcohol infusion ramp (4 mg/dL/min) to bring BrAC to 60 mg/dL. Min 110-140: Alcohol+OT or Alcohol+PL battery assessing initial response to alcohol during BrAC clamp at 60 mg/dL. Min 180-182.5: Booster dose of OT or PL. Min 200-230: Alcohol+OT or Alcohol+PL battery assessing adapted response to alcohol during BrAC clamp at 60 mg/dL.

Session procedures: Alcohol Clamp (Figure 3). Clamp sessions begin with a baseline battery lasting approximately 30 min and consisting of the Stop Signal Task (a motor impulsivity task that has demonstrated sensitivity to alcohol exposure); a subjective perceptions assessment, including craving; a side effects questionnaire; the Alcohol Purchase Task (a cognitive test providing measures of behavioral economics, revised for use during iv infusion); and the Stroop Test of mental concentration (accuracy and speed stating the color of a series of words printed in colors different from the colors they actually name). The battery is repeated after an initial dose of OT or PL, and at the beginning and end of a 2 h clamp, with booster doses of OT or PL 20 min prior to each of the clamp batteries. The dosing schedule of oxytocin relative to testing is derived from studies suggesting onset of effects in approximately 30 minutes and a duration of approximately 60 minutes⁴⁸⁻⁵¹. The first dose of OT or PL will consist of 10 intranasal puffs [insufflations] alternating every 30 seconds between nostrils, delivering in total 40 IU of OT in 1 ml of solution or 1 ml of PL solution. A 20-30 min drug absorption period follows the first dose; booster doses of 24 IU of OT will be given 20 min prior to each of the remaining 2 test batteries. During the intervals between test batteries, the participant will be free to rest, read, or use an electronic device for entertainment.

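### Aim 1 does not name its alcohol-free reference battery; read literally, its contrast mixes any direct oxytocin effect with a change in alcohol response

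*Combined protocol and SAP*

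**What the plan says.** The point concerns the clamp arm only.

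**Analysis text.** Hypothesis 1 in Section 12.0 is that "participants exhibit greater effects of alcohol when tested with OT compared to PL and each with respect to its own baseline assessment". Section 3.1 words the endpoint in the same way: "Compared to their performance under PL and respective baseline assessment, participants given intranasal OT will show" a greater alcohol-related disturbance on one or more of the measures. Neither section names a battery or a time. The general statement on paired t-tests in Section 12.0 adds only "accommodating baseline assessments as appropriate for the specific measures". The measure-by-measure predictions under Aim 1 compare OT with PL and mention no reference.

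**Schedule.** In Section 7.0, "Clamp sessions begin with a baseline battery lasting approximately 30 min", and then "The battery is repeated after an initial dose of OT or PL, and at the beginning and end of a 2 h clamp". The Figure 3 timeline gives four batteries:

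- Baseline, minutes 0 to 30, before any drug.
- OT/PL, minutes 60 to 90, after the first dose and before alcohol.
- Initial clamp response, minutes 110 to 140.
- Adapted clamp response, minutes 200 to 230.

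The study calendar in Section 8.0 also lists the baseline and OT/PL blocks separately.

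**Other wording that bears on this.** Section 2.1 says "Cognitive, motor and subjective responses will be tested prior to, at the beginning, and at the end of a steady-state alcohol clamp", which fits either alcohol-free battery. Section 2.2 distinguishes baseline from control assessments for the clamp, but only under Aim 2 and without defining either term.

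**The concern.** Hypothesis 1 is about the response to alcohol: does alcohol do more when OT is on board? To isolate that, the alcohol-free reference should already contain whatever OT does by itself. The only battery the schedule calls baseline comes before the drug, so it does not.

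If that battery is the reference, a plain OT effect on speed, errors or ratings would be labelled altered tolerance. A direct effect in the opposite direction could hide a real change. The study's stated purpose is to supply data for a larger, properly powered trial, so a mixed contrast would pass the wrong effect forward.

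The open choice also adds flexibility. Two references times two clamp batteries gives four possible contrasts per measure, under a rule that accepts a finding on one or more measures.

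**Working it through.** The plan gives no power, alpha or effect-size figure for this contrast, so there is none to reproduce.

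**Algebra.** For one measure, let B be the pre-drug score, τ1 and τ2 the time and practice shifts common to both sessions, A the alcohol effect under PL, d the direct OT effect at minutes 60 to 90, k the fraction of d present in the clamp battery, and T the change in alcohol response caused by OT.

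| Battery | OT session | PL session |
|---|---|---|
| Pre-drug | B | B |
| OT/PL | B + τ1 + d | B + τ1 |
| Clamp | B + τ2 + A + kd + T | B + τ2 + A |

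Each contrast is OT minus PL:

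- Clamp minus pre-drug: **T + kd**
- Clamp minus OT/PL: **T − (1 − k)d**
- OT/PL minus pre-drug: **d**

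Time and practice cancel in all three. The direct effect does not cancel in the first, and it cancels in the second only if k = 1. If d = 0, the first two both estimate T.

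**Examples, in SDs of the paired difference:**

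- d = 0.5, T = 0, k = 1: the pre-drug contrast is 0.5 (apparent change); the OT/PL contrast is 0.
- d = −0.5, T = 0.5, k = 1: the pre-drug contrast is 0 (real change hidden); the OT/PL contrast is 0.5.
- d = 0.5, T = 0, k = 0.6: 0.6 × 0.5 = +0.3 against −0.4 × 0.5 = −0.2. Both are off.

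**Rejection rates.** Inputs from Section 7.0: a minimum of 5 completers per arm; 7 is about half of the upper target of 15. Assumed, because the documents do not state them: two-sided alpha 0.05, d = 0.5 or 1.0, T = 0, k = 1, and the same SD of the paired difference for both references. The rate is P(|t| > critical value) for a noncentral t with n − 1 degrees of freedom and noncentrality shift × √n.

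| n | d | Noncentrality | Pre-drug reference | OT/PL reference |
|---|---|---|---|---|
| 5 | 0.5 | 0.5 × √5 = 1.12 | 14.1% | 5% |
| 5 | 1.0 | 1.0 × √5 = 2.24 | 40.1% | 5% |
| 7 | 0.5 | 0.5 × √7 = 1.32 | 20.1% | 5% |
| 7 | 1.0 | 1.0 × √7 = 2.65 | 60.0% | 5% |

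A simulation of 20,000 runs gave 14.4%, 39.8%, 19.4% and 59.5% for the pre-drug reference, and 4.9% to 5.0% for the OT/PL reference.

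**Sensitivity to k.** Full persistence favours the OT/PL reference. With k = 0.40 and d = 1.0, the shifts are 0.40 (pre-drug) and −0.60 (OT/PL), and the ranking reverses: 11% against 18% at n = 5, and 15% against 27% at n = 7.

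**Can the documents fix k?** No. The first dose is described as "delivering in total 40 IU of OT in 1 ml of solution or 1 ml of PL solution", and the boosters as 24 IU. One comes as an "OT/PL booster dose at the beginning of a 15 min alcohol infusion ramp" and one at minute 180. Section 7.0 puts onset at about 30 minutes and duration at about 60. Take a crude on/off effect, with duration counted from onset:

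- Clock from the start of dosing: 30 active minutes in the OT/PL battery, 30 in the initial and 20 in the adapted, so k = 30/30 = 1.00 and 20/30 = 0.67.
- Clock from the end of dosing (first dose ends at minute 35; boosters last 2.5 minutes, assumed for the one at minute 90): 25, 30 and 17.5 active minutes, so k = 30/25 = 1.20 and 17.5/25 = 0.70.
- Onset of 20 minutes, the lower end of the stated absorption period: adapted k = 30/30 = 1.00.
- Clock from the start, duration counted from dosing, and effect proportional to dose (24/40 = 0.6): k = 20 × 0.6/30 = 0.40 for both clamp batteries.

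The answer depends on the model chosen, and k can exceed 1 through timing alone.

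**The case against.** The best defence is that the plan is open rather than wrong. Section 12.0 leaves baseline handling to suit each measure, Section 2.1 fits both alcohol-free batteries, and Section 2.2 suggests that the investigators had a second comparator in mind. The study is exploratory, and every battery is collected in both sessions, so any contrast can still be computed later. No direct OT effect on the Stroop or Stop Signal tasks is reported, and the background cites one study in which OT did not reduce self-reported craving. Craving is also a weak example, because Section 3.2 places it under Aim 2, where a direct effect is itself of interest.

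Much of this stands. It limits the consequence and rules out saying that the analysis will be biased. It does not supply the missing definition: the Section 2.2 terms are undefined and belong to Aim 2. A zero direct effect is not safe to assume either, since the background also cites an OT effect on interoceptive accuracy in heavy drinkers.

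Three stronger readings are tempting and are not supported:

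- *The plan has committed to the pre-drug reference.* The schedule's use of the word points that way, but no section rules out the OT/PL battery.
- *The OT/PL battery is simply the correct reference.* Dose and timing differ between that battery and the clamp batteries, so the direct effect need not be equal.
- *The protocol's onset, duration and doses bound the persistence, so the two contrasts bracket the truth.* The bounds come from an added on/off model, and timing from the end of dosing already gives k = 1.20. Even with k between 0 and 1, the bracket holds only in expectation, which is little comfort with 5 to 7 participants.

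**Conclusion.** The concern holds as a conditional gap in the analysis plan, not in data collection. Following the words of Sections 3.1 and 12.0 with the schedule's meaning of baseline gives a combined effect, from which altered tolerance cannot be claimed alone. That conclusion needs only the algebra and the timeline.

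Its practical size is unknown, because the documents give neither the direct OT effect nor its persistence into the clamp. The tabulated rejection rates illustrate assumed values and do not forecast this trial. The point is worth fixing before analysis. Confidence is medium, since it matters only if a direct effect exists.

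**What to change.** In Sections 3.1 and 12.0, for the clamp arm and before analysis:

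1. Name the reference battery and the clamp battery (initial or adapted) for each Aim 1 measure.
2. Report clamp minus OT/PL battery alongside clamp minus pre-drug battery, each as OT minus PL.
3. Report OT/PL battery minus pre-drug battery, OT minus PL, as the direct drug effect.
4. Label the pre-drug contrast as the combined effect, and do not claim altered tolerance from it alone.
5. State that the OT/PL reference removes the direct effect only if that effect is similar at minutes 60 to 90 and during the clamp, which the differing doses and timings do not guarantee. If a sensitivity range for persistence is shown, state its assumptions and let it go above 1.

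The cost is wording: all four batteries are already scheduled in both sessions, and no procedure changes. The downside is a few more contrasts in a very small exploratory sample, which should be presented as estimates with intervals and not as further chances of success.

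### Does placing one subjective-effects-and-craving prediction under both aims let a single result count twice?

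*Combined protocol and SAP*

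**What the plan says.** Section 12.0 gives one sentence for this item and prints it under both hypothesis testing plans: "Participants will report weaker subjective effects of alcohol and higher craving under PL compared to OT". For Aim 1 the rule is "we predict the following differences in one or more of the following measures". The Aim 2 rule is also met by any one listed measure.

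The other sections place the content as follows.

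- **Section 2.0** shares it: "Tolerance to and motivation for alcohol will be assessed with sensitive tests of subjective response and cognitive function".
- **Section 2.2 (Aim 2)** puts both parts under motivation. It says "Motivation will also be assessed by measures given during the clamp" and includes "measures of subjective perception and craving for alcohol".
- **Section 3.1 (Aim 1)** lists "greater alcohol-related perturbation of the subjective response to alcohol, the Stroop test, and Stop Signal task performance". Craving is not named.
- **Section 3.2 (Aim 2)** lists "During the BrAC clamp, altered APT derived behavioral economic indices and/or reduced subjective craving for alcohol". Strength of subjective effects is not named.
- **Section 7.0, clamp sessions,** shows that both parts come from one instrument: "a subjective perceptions assessment, including craving".
- **Section 7.0, self-administration sessions,** gives the same assessment before the first dose, just before self-administration starts, and then every 20 minutes. The study calendar in section 8.0 agrees.

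**The concern.** Sections 2.0, 2.2 and 12 share the measure across the aims, while section 3 divides it. Section 12 joins the two parts with a plain conjunction. It does not say whether both must change, which arm supplies the Aim 2 version, or whether one result may support both aims.

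Because any single measure can satisfy an aim, a difference on one questionnaire in the clamp arm could be presented as evidence on tolerance and again as evidence on motivation. The study exists to justify a larger trial on tolerance, motivation or both. That trial's designers might then believe they have two independent lines of support when they have one.

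**Working it through.** **The plan's own figures.** There are none to reproduce. Section 12.0 specifies paired t-tests and gives no significance level, sidedness, multiplicity rule or target power. The figures below are illustrations. They assume no drug effect, 0.05 per test and independent measures.

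**Inputs (section 12.0).**

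- Measures for Aim 1 alone: stop-signal reaction time, Stroop time, Stroop errors (3).
- Measures for Aim 2 alone: four named Alcohol Purchase Task (APT) indices, cumulative work, alcohol exposure (6). The APT list is open-ended, so 4 is an assumption.
- Common to both: subjective effects and craving (2 parts).
- Distinct measures: 3 + 6 + 2 = 11.

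**Formula.** P(both aims) = P(Aim 1) + P(Aim 2) − P(at least one aim).

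**Shared item, parts scored separately.**

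- Aim 1: 1 − 0.95^5 = 0.226
- Aim 2: 1 − 0.95^8 = 0.337
- At least one: 1 − 0.95^11 = 0.431
- Both: 0.226 + 0.337 − 0.431 = 0.132

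**Shared item, both parts required.** The item's false-positive chance is 0.05² = 0.0025.

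- Aim 1: 1 − 0.9975 × 0.95^3 = 0.1448
- Aim 2: 1 − 0.9975 × 0.95^6 = 0.2667
- At least one: 1 − 0.9975 × 0.95^9 = 0.3713
- Both: 0.1448 + 0.2667 − 0.3713 = 0.040

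**Divided as in section 3, one part per aim.**

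- Both: (1 − 0.95^4)(1 − 0.95^7) = 0.185 × 0.302 = 0.056
- At least one: 1 − 0.95^11 = 0.431

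**Coarser count.** Stroop and APT are counted once each, which leaves 2 measures for Aim 1 alone, 3 for Aim 2 alone and 2 shared parts.

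- Separate parts, both aims: 0.0975 + 0.9025 × 0.0975 × 0.1426 = 0.110
- Both parts required, both aims: 0.0025 + 0.9975 × 0.0975 × 0.1426 = 0.016
- Divided, both aims: 0.1426 × 0.1855 = 0.026
- At least one aim: 1 − 0.95^7 = 0.302 with separate parts, shared or divided; 1 − 0.9975 × 0.95^5 = 0.228 if both parts are required

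| Count | Reading of the shared item | Both aims: shared → divided | At least one aim: shared → divided |
|---|---|---|---|
| 11 measures | parts separate | 13.2% → 5.6% | 43.1% → 43.1% |
| 11 measures | both required | 4.0% → 5.6% | 37.1% → 43.1% |
| 7 measures | parts separate | 11.0% → 2.6% | 30.2% → 30.2% |
| 7 measures | both required | 1.6% → 2.6% | 22.8% → 30.2% |

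At 0.025 per test with 11 measures, the both-aims figures are 5.9% → 1.6% (separate) and 1.1% → 1.6% (both required). The pattern is the same.

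**What the table shows.** Dividing the item helps on one reading and hurts on the other. It never lowers the chance that at least one aim is declared, which is the quantity that matters under section 2.0, where evidence for either outcome suffices.

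**Whether it must be the same result.** Sections 2.2 and 3.2 point to the clamp for the Aim 2 version, but section 12.0 does not restrict it. Ratings from the self-administration arm come from different participants, since each person is assigned to one condition. If those ratings served Aim 2, the two results would not be one result counted twice.

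**The case for a change.** The best case for a change is that these are conflicts between current sections, and that calling a study exploratory does not settle which aim a measure belongs to. Aligning the text would cost only words and would remove a choice that could otherwise be made after the results are seen. If the parts are scored separately, dividing them cuts the both-aims chance by more than half. That survives correlation: with correlation 0.6 within each arm and 5 participants per arm, simulation gave 12.8% shared against 7.6% divided.

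Part of this stands. The sections disagree, and section 12.0 is silent on the joint or separate reading, the arm and the counting. Item-level scoring may be in the assessment form listed in the appendix, which is not shown.

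The rest is weaker.

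- The cut depends on a reading that the literal conjunction does not favour. With both parts required, the same correlated setting moves the other way, from 6.2% to 7.8%.
- The plan is not without a reason for sharing. Section 1.0 describes tolerance as driving escalating intake, expects lower tolerance to weaken a cause of relapse, and treats alcohol seeking as tied to tolerance. The link can be debated, but with sections 2.0 and 2.2 it suggests that sharing was intended and that section 3 is the outlier.
- Confining both parts to the clamp arm would leave the self-administration ratings outside both aims, which is a real cost.

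**Conclusion.** No change to the plan is called for. The wording is inconsistent across sections 2, 3 and 12, but the inconsistency alters no estimate, test or decision. Subjective effects and craving are collected and compared between oxytocin and placebo under either filing. No conclusion requires both aims, and the study offers its results as groundwork for a properly powered trial. Keeping the measure shared and assigning each part to one aim are both defensible. An analyst reporting the two parts separately, naming the arm and noting that one instrument bears on both aims would give readers what they need.

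The effect on the both-aims chance has no consistent sign: 13.2% falls to 5.6% on one reading, and 4.0% rises to 5.6% on the other. These figures rest on an assumed 0.05 per test, independence and a count of 11 measures. Other assumptions move the levels, but the opposite directions also appear with the coarser count, at 0.025 and with correlated measures.
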